5. STUDY PROCEDURES AND ASSESSMENT

5.1. DEFINITIONS OF STUDY PROCEDURES

5.1.1. Informed Consent

Prior to initiation of any study procedures, each subject will undergo an Informed Consent process in which the subject voluntarily confirms their willingness to participate in the trial, after having been informed of all aspects of the trial relevant to their decision to participate. The investigator, or a person designated by the investigator, will fully inform the subject of all pertinent aspects of the trial. In addition, the investigator, or a person designated by the investigator, or a person designated by the finter the subject that he is free to refuse to enter the study or to withdraw from the study at any time, for any reason.

The Informed Consent Form (ICF) approved by the IRB/EC will contain a description of the study's purpose, procedures, inconveniences and potential risks, and anticipated benefits.

Prior to a subject's participation in the trial, an ICF will be signed and personally dated by the subject and by the person who conducted the Informed Consent discussion.

If a subject is unable to read, he/she may not participate in the study.

Prior to participation in the trial, the subject will receive a copy of the signed and dated written ICF. During participation in the trial, the subject will receive a copy of the signed and dated consent form updates.

The investigator should document in the source data that the Informed Consent was signed prior to subject's participation in the study and according to the International Conference on Harmonization Good Clinical Practice (ICH-GCP) guidelines, as described above.

5.1.2. Medical History

Subjects' medical history should be fully documented at Screening Day (14 through 1 day prior to baseline), to ensure compliance with study inclusion criteria and the absence of circumstance mentioned in the exclusion criteria. Medical history information must include, but not be limited

to, past and present medical conditions, concomitant non-drug treatments and hypersensitivity to drugs.

5.1.3. Concomitant Medication

All concomitant medication given 1 month prior to study entry, including blood and blood products, dietary supplements, and non-prescription drugs will be listed at screening/baseline. Each entry will include the treatment's start date, treatment name (Generic), reason for use, dosing regimen (dose and frequency of use), route of administration, and stop date (if applicable). The clinical significance of the medication use will be decided by the investigator. Study subjects will be routinely questioned for changes in the administration of concomitant medication during the trial and changes should be updated from medical records as well.

5.1.4. Physical Examination

The investigator (or medically qualified nominee) will conduct a complete physical examination, height and weight measurements at Screening Day (performed 14 through 1 day prior to baseline). Clinically significant abnormal findings except overweight and obesity should be discussed with the Sponsor.

Additional physical examination to assess subject's safety will be performed on study visit on Day 28 and 56 following treatment.

5.1.5. Pain Measurement

Local lipoma pain, as determined by the Comparative Pain Scale, will be measured at Baseline visit prior to injection, in order to establish a baseline for comparison following drug injection. Subjects will complete a comparative pain scale score for each lipoma selected for injection.

Additional pain measurements for the treated lipomas will be performed on study visit Days 28, 56, and 84 after injection.

A description of the comparative pain sale is presented in Appendix II.

5.1.6. Quality of Life Assessment

QOL will be measured in subjects at Baseline visit in order to establish a baseline for comparison after drug injection. For this purpose, the Short Form 36 questionnaire (See Appendix III) will be used to evaluate the improvement in the QOL of active vs. placebo group subjects.

Additional assessment of QOL will be performed on the Day 84 visit.

5.1.7. Vital Signs Measurements

Subjects' vital signs will be measured at Screening Day (performed 14 through 1 day prior to baseline) in order to ensure compliance with study inclusion criteria.

Vital signs measurements will include systolic and diastolic sitting position blood pressure, pulse rate, respiratory rate, and body oral temperature.

Additional vital signs measurements to assess subject's safety will be performed on baseline visit (Day 0) prior to drug injection, $2h \pm 30$ min following drug injection, the following day (Day 1) after drug injection ($24h \pm 2h$) and on study visits Day 28 and Day 56 following injection.

5.1.8. Serology assay

Assays for Hepatitis C virus (HCV), Hepatitis B Surface Antigen (HbSAg), and human immunodeficiency virus (HIV) will be conducted on Screening Day 1 (performed 14 through 1 day prior to baseline) in order to ensure compliance with study inclusion criteria.

5.1.9. Clinical Laboratory tests

Clinical laboratory tests will be conducted on Screening Day (performed 14 through 1 days prior to baseline) in order to ensure compliance with study inclusion criteria. Additional studies will be conducted on different study visits according to schedule as written below for each set of tests. The maximum total blood volume will be 30 mL per visit. Every out-of-range value will be assessed by a physician and deemed as either clinically significant or clinically not significant. Values that represent a change from baseline in subject's medical status according to the laboratory normal ranges will be adequately documented as an AE as described in Section 8.

5.1.9.1. Hematology

Hematology tests will be conducted at Screening Day (performed 14 through 1 days prior to baseline) in order to ensure compliance with study inclusion criteria. Additional Hematology testing will be conducted to assess subject's safety on study visit Day 1 and Day 28 following injection.

Hematology tests will include Complete blood count (CBC) including White blood cell (WBC) differential values, D-dimer, Fibrinogen and coagulation (International normalized ratio (INR), Partial thromboplastin time (PTT) and Prothrombin time (PT)).

In case a specific subject demonstrates elevated blood levels in one or more of the tested parameters, this subject will be followed up on day 56 to confirm return to normal levels.

5.1.9.2. Serum Chemistry Analysis

Testing of blood chemistry values will be conducted on Screening Day (performed 14 through 1 days prior to baseline) in order to ensure compliance with study inclusion criteria.

Additional Serum Chemistry testing will be conducted on Day 0 (before injection), $24hr \pm 2hr$ following injection and on study visit Day 1 and Day 28 following injection.

Serum chemistry will include:

Albumin, Albumin/Globulin Ratio (calculated), Alkaline Phosphatase, ALT, AST, BUN/Creatinine Ratio (calculated), Calcium, Carbon Dioxide, Chloride, Creatinine with GFR Estimated, Globulin (calculated), Glucose, Potassium, Sodium, Total Bilirubin, Total Protein, Urea Nitrogen. In addition, Amylase, Lactate dehydrogenase [LDH], Creatine-kinase MM [CK-MB], Creatine phosphokinase [CPK], Gamma-glutamyl transferase [GGT], Alkaline phosphatase [ALP]) and C-reactive protein [CRP] will be tested.

In case a specific subject demonstrates elevated blood levels in one or more of the tested parameters, this subject will be followed up on day 56 to confirm return to normal levels.

5.1.9.3. Urinalysis

Urinalysis will be conducted at Screening Day (performed 14 through 1 days prior to baseline) in order to ensure compliance with study inclusion criteria and to allow differential diagnosis in case of urinary tract associated AE. Additional urinalysis testing will be conducted on study visit Day 1 and 28 following injection.

Urinalysis will include: Protein, Red blood cells (RBC), WBC, Blood, Glucose, Ketone bodies, Bilirubin, Urine specific gravity and pH.

In case a specific subject demonstrates elevated blood levels in one or more of the tested parameters, this subject will be followed up on day 56 to confirm return to normal levels.

5.1.9.4. Lipid profile

Lipid profile will be conducted on Screening Day (performed 14 through 1 days prior to baseline) in order to allow differential diagnosis in case of lipid circulation in blood following injection.

Additional lipid profile testing will be conducted on Day 1 visit following injection.

Lipid profile will include: Total Cholesterol (TC), High Density Lipoprotein (HDL), Low Density Lipoprotein (LDL), Triglycerides (TG) and Fasting glucose.

5.1.10. ECG

Subjects' ECG will be performed on Screening Day (performed 14 through 1 days prior to baseline) in order to ensure compliance with study inclusion criteria. ECG is to be performed on at least a triplicate of heartbeats for all measurements and will be recorded at a speed of 25 mm/sec. Additional ECGs will be performed at Day 1 and Day 28 visits following injection.

Computerized ECG analysis will include: Heart rate, Rhythm, PR interval, QRS axis, and QRS duration. The corrected QT interval and QTc will be calculated manually according to the Frederica formula. ECG will be recorded at a standard speed of 25 mm/sec and standard amplitude of 10 mm/mV.

5.1.11. Draize Score

Subjects' skin irritancy will be evaluated by Draize score. Draize score will be assessed for each selected lipoma for injection before treatment in order to establish a baseline for comparison following drug injection.

Additional skin irritancy evaluation to assess skin condition will be performed on baseline visit $2h \pm 30$ min following injection and on study visits Day 1, 28, 56 and 84 following injection. Skin irritancy observations at the injected sites will be scored using the Draize scale for scoring skin reaction:

Erythema and eschar formation		Edema formation		
No erythema 0		No edema	0	
Very slight erythema (barely perceptible)	1	Very slight edema (barely perceptible)	1	
Well defined erythema	2	Slight edema (edges are well defined by definite raising)	2	
Moderate to severe erythema	3	Moderate edema (raised approximately 1mm)	3	
Severe erythema (beet redness) to slight eschar formation (injuries in depth)	4	Severe edema (raised more than 1mm extending beyond area of exposure)	4	

5.1.12. Photography of lipomas

Documentation of the lipoma location and its skin condition in the injected area will be conducted at Screening Day (performed 14 through 1 days prior to baseline). Additional photography will be performed at Baseline visit pre injection, Day 28, Day 56 and Day 84 visit.

Photography with a digital camera will include:

- a. A picture from above will be taken perpendicular to lipoma top at a minimum distance of 5 cm or less and the distance noted and repeated throughout the study
- b. A side picture will be taken parallel to lipoma to at a minimum distance of 5 cm or less and the distance noted and repeated throughout the study.

[figure not shown]
5.1.13. Imaging: Ultrasound (US)

Evaluation of Ultrasound will be conducted at Screening (performed 14 through 1 days prior to baseline) to ensure compliance with study inclusion criteria and establishing a baseline. Nodule size and tissue characteristics will be documented. Additional US will be performed on Day 0. In case of screening visit that will be conducted only one day before Baseline, ultrasound and photographs at Baseline visit are optional. The ultrasound parameters and phots collected at screening will be used at Baseline visit. In case the study personnel decide to inject different lipomas than those that were chosen at the screening visit, then ultrasound evaluation is mandatory on Day 0. Additional US measurements for the injected lipomas will be done at Days 28, 56 and 84 visits and the change in dimensions will be compared to the recorded dimensions at baseline.

Ultrasound imaging will be conducted on Day 0 (before injection) in order to ensure proper dose injection according to measured nodule size/diameter. In case of screening visit that will be conducted only one day before Baseline, ultrasound and photographs at Baseline visit are optional. The ultrasound parameters collected at screening will be used at Baseline visit.

Assessment of nodular size will be by diameter (mm) and surface (mm²) in three dimensions as illustrated below:

- Height
- Width
- Length

5.1.14. Adverse Events

The information obtained during periodic subject questioning, review of subject's compliance record, physical examinations, vital signs measurements, blood testing, and by any other means will be evaluated in light of baseline medical data and thus provide the basis for adverse events identification and grading.

Thirty-eight (38) subjects (19 active and 19 placebo) will be injected with a dose of up to 240 mg/subject in the RZL-012 group or with up to 4.8 mL of vehicle in the placebo group.

The AEs reported during the trial will be graded (see Section 9), documented, and assessed in light of their clinical significance and relation to investigational product. In addition, the following information regarding the AE must be obtained: AE description, start date, end date (if applicable) or ongoing, severity, seriousness, relationship to study drug, outcome (e.g., resolved / unresolved), and action taken (e.g., concomitant medication). The sponsor or the sponsor representative will provide information regarding serious adverse event (SAE) expectedness based on data included in the IB. AE monitoring will be conducted throughout subject's participation up to 84 days after injection.

5.1.15. Evaluation of Response

Evaluation of response will be conducted on Days 28, 56, and 84 following injection.

5.1.15.1. Evaluation of Primary Endpoints

5.1.15.1.1. Ultrasound to assess lipoma/nodule dimension after treatment

Local fat reduction will be evaluated by ultrasound. Local fat reduction is defined as the reduction in nodule height at the injected area as compared to baseline and as a function of treatment (active/placebo). Ultrasound of the injected lipomas/nodules will be conducted at baseline and on Days 28, 56 and 84 following treatment.

5.1.15.2. Evaluation of Secondary Endpoints

5.1.15.2.1. Pain – A key secondary endpoint

Improvement in local pain will be assessed by pain scoring of each lipoma/nodule on study Days 28, 56 and 84 following injection and comparing to baseline assessments. This evaluation will be done using the comparative pain scale.

5.1.15.2.2. Safety monitoring

Safety and tolerability will be assessed, according to definitions and guidelines, by the medical staff (e.g., PI, site coordinator, and study nurse) and the study subjects:

- 1. AEs and SAEs, including severity, relation to study treatment and classification by whether or not these events comprise intolerable side effects.
- 2. Physical exams, Draize score and vital signs measurements.
- 3. Urine testing.
- 4. Blood laboratory testing for changes in hematology and chemistry values.
- 5. Lipid profile.
- 6. ECG.

Subjects questioning - full medical history during screening, routine AE reporting and tolerability monitoring.

5.1.15.3. Exploratory endpoints

5.1.15.3.1. Improvement in QOL

QOL of RZL-012 treated vs. placebo subjects will be assessed 84 Days vs. baseline visit in order to compare whether there is an improvement in subject's QOL as a function of treatment.

5.1.15.4. Compliance Monitoring

Compliance monitoring will include the following procedures:

• Compliance assessment by site coordinator at the study visit, including but not limited to subject questioning.

5.1.15.5. Dispensing of RZL-012 Investigational Product

The RZL-012 investigational product will be dispensed to the study site under monitored conditions by Nextar Ltd. All procedures connected to investigational product's allocation (kits received at site, returned kits) will be properly documented, dated and signed in a designated site folder to allow full product tracking. Source documents will be kept for the duration required by local regulations and ICH-GCP (whichever is longer).

5.1.15.6. Questioning of Study Subjects

Questioning of study subjects during site visits and any unscheduled conversations (e.g., by phone) with site staff will be fully documented in subject file. Whenever possible, subject questioning should include, but not be limited to, inquiring information regarding occurrence and severity of AEs, treatment tolerability and compliance to future scheduled procedures and visits.

5.2. STUDY VISITS

Study visits will be fully documented in the CRF as described in Section 11. Documentation will be completed in a timely manner and within 5 working days to ensure protocol adherence and compliance with ICH-GCP.

5.2.1. Screening Procedures

All information collected and documented during screening procedures will be reviewed to ensure eligibility in reference to study inclusion and exclusion criteria, and fully documented in subject file.

Screening visit should be performed 14 days ahead and no later than 1 day prior to baseline visit.

Study Screening Day procedures will include the following:

- Informed Consent Section 5.1.1
- Medical History Section 5.1.2
- Concomitant Medication Section 5.1.3
- Physical Examination Section 5.1.4
- Vital signs Measurement –Section 5.1.7
- ECG Section 5.1.10
- Serology -5.1.8
- Clinical laboratory tests Section **Error! Reference source not found.**
- Photography of injected lipomas Section Error! Reference source not found.
- Ultrasound to measure lipoma/nodule dimensions Section 5.1.13

Subjects may be rescreened if they were screened and did not completed their blood and urine tests and not dosed within 14 days. The following procedures will be performed: Clinical Laboratory Tests (hematology, serum chemistry, and urinalysis), vital signs, Draize score and photography.

5.2.2. Study Randomization

Subjects will be randomized to each study group, i.e., investigational therapy or control, according to a predefined randomization scheme in a ratio of 1:1 (active:placebo) among the 4 clinical sites. The investigational therapy group will be treated with RZL-012 and the control group will be treated with the same formulation (vehicle) as with RZL-012, absent active medication.

Assignment to study group will be disclosed only after subject eligibility is confirmed and immediately before treatment initiation. The investigator and the clinical staff will be masked to the treatment. The subjects will also be blinded and will not know whether he or she is injected with active or placebo treatment.

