Sample Size	This study is a Phase 2b trial. A total of 38 evaluable DD subjects from 3-4 centers will be included in the study (19 will be injected with RZL-012 and 19 will receive placebo). Subjects will be followed up for 84 days after injection.						
	Once the study ends and codes are opened, the 19 placebo-treated subjects will be offered the option of receiving treatment with RZL-012. Subjects who choose this will be followed up for an additional 84 days.						
	The statistical considerations described below relate to the placebo-controlled phase of the study. Based on primary endpoint:						
	Subjects will be randomized into two groups in a 1:1 ratio.						
	The rationale for sample size calculation was based on data from Raziel's open label phase 2a study (Study $\#RZL-012$ -FD-P2aUS-001) in which a reduction in lipoma/nodule height of about 55% was demonstrated in the treatment group. This phase 2a study did not include a placebo group but studies reported by other groups show an average reduction from baseline in lipoma/nodule height of about 7% in the placebo group. Taking these numbers into consideration an effect size of 0.96 is expected (effect size = expected effect size in treated (0.55) – expected effects size in placebo group (0.07)/expected standard deviation (0.5)).						
	Sample size justification:						
	A sample size of 19 in each group (total sample size of 38) will have 80% power to detect a difference in means of 48 (the difference between a Group 1 mean, μ_1 , of 55 and a Group 2 mean, μ_2 , of 7) assuming that the common standard deviation is 50 using a two-group t-test with a 0.05 two-sided significance level.						
	Based on key secondary endpoint:						
	Subjects will be randomized into two groups with a 1:1 ratio.						
	The rationale for sample size calculation was based on data from our open label phase 2a study (Study #RZL-012-FD-P2aUS-001) in which reduction in lipoma/nodule pain score of about 76% was demonstrated in the treatment group. Our phase 2a study did not include a placebo group but pain studies reported by other groups, show a range of reduction in pain score from +10%60% in the						

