10.2. STUDY ENDPOINTS

10.2.1. Analysis of Efficacy for Primary Endpoint

• Analysis per patient (based on 4-8 lipomas/nodules per patient)

The two-sample T-test or Non-parametric Wilcoxon-Mann-Whitney Rank sum test for independent samples (as is appropriate) will be applied for testing the statistical significance of the difference between study groups in percent reduction of lipoma/nodule height at day 84 after injection vs. baseline.

Analysis of covariance (ANCOVA) model will be applied in order to identify covariate parameters suspected as related to reduction in lipoma/nodule height and in order to test the differences in percent reduction of lipoma/nodules height between the treatment groups adjusted to the above covariates.

• Analysis per lipoma/nodule (based on 4-8 lipomas/nodules per patient)

The MMRM model (Mixed-effect model for repeated measures) will be applied for analyzing the difference between the groups in percent reduction of lipoma/nodule height from baseline to day 84 and adjusted for the above covariates as appropriate.

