10.3. SAMPLE SIZE JUSTIFICATION

Based on primary endpoint:

The rationale for sample size calculation was based on interim data from Raziel's open label phase 2a study (Study #RZL-012-FD-P2aUS-001) in which reduction in lipoma/nodule height of about 55% was demonstrated in the treatment group. Raziel's phase 2a study did not include a placebo group but studies reported by other groups (15,16) show an average reduction from baseline in lipoma/nodule height of about 7% in the placebo group. Taking these numbers into consideration Raziel expect an effect size of 0.96 (effect size = expected effect size in treated (0.55) – expected effects size in placebo group (0.07)/expected standard deviation (0.5)).

Sample size justification:

A sample size of 19 in each group (total sample size of 38) will have 80% power to detect a difference in means of 48 (the difference between a Group 1 mean, μ 1, of 55 and a Group 2 mean, μ 2, of 7) assuming that the common standard deviation is 50 using a two-group t-test with a 0.05 two-sided significance level.

Based on key secondary endpoint:

The rationale for sample size calculation was based on data from our open label phase 2a study (Study #RZL-012-FD-P2aUS-001) in which reduction in lipoma/nodule pain score of about 76% was demonstrated in the treatment group. Our phase 2a study did not include a placebo group but pain studies reported by other groups (17) show a range of reduction in pain score from +10% - 60% in the placebo group. Based on Geography, study size and length we selected an expected reduction from baseline of 25% in lipoma pain in our placebo group. Taking these numbers into consideration we expect an effect size of 1.02 (effect size = expected effect size in treated (0.76) – expected effects size in placebo group (0.25)/expected standard deviation (0.5)).

Sample size justification:

A sample size of about 19 in each group (total sample size of 38) will have 80% power to detect a difference in means of 51 (the difference between a Group 1 mean, μ 1, of 76 and a Group 2 mean, μ 2, of 25) assuming that the common standard deviation is 50 using a two-group t-test with a 0.05 two-sided significance level.

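### Neither the randomisation list nor the patient-level test is tied to site; blocking within site and fitting site together is a cheap gain in precision if sites differ

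*Combined protocol and SAP*

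**What the plan says.** - **Allocation.** Section 5.2.2 assigns subjects "according to a predefined randomization scheme in a ratio of 1:1 (active:placebo) among the 4 clinical sites". Stratification or blocking by site is not mentioned.
- **Patient-level test.** Section 10.2.1 names "The two-sample T-test or Non-parametric Wilcoxon-Mann-Whitney Rank sum test for independent samples", whichever is appropriate, for percent reduction in height at Day 84. Section 10.2.2 repeats this for pain. Neither has a site term.
- **Other planned models.** Both sections add a patient-level ANCOVA, whose stated uses are to find related covariates and to adjust for them, and a lipoma-level MMRM adjusted for the same covariates. No covariate is named, and none of these analyses is designated as the primary one.
- **Site in the analysis text.** Section 10 does not name site as a factor, stratum or covariate.
- **Number of sites.** Sections 3.1 and 5.2.2 and the Study Sites row of the synopsis give 4. The Sample Size row of the synopsis says "A total of 38 evaluable DD subjects from 3-4 centers will be included in the study". There is no rule for pooling small sites.

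**The concern.** Outcomes in a multi-centre trial may vary by site, and this protocol leaves room for that. Sections 5.1.13 and 5.1.15.1.1 set no central reading or operator rule for the ultrasound. Each subject has 4 to 8 lipomas injected, and study personnel may change the selection after screening. Topical anaesthetic before dosing is optional (Section 7.1).

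If sites do differ, what happens depends on the list:
- **Balanced within site.** Site differences cancel out of the treatment contrast but stay in the t-test's error term. The standard error is then too large and the test is conservative.
- **Not balanced within site.** With about 9 or 10 subjects per site, uneven splits are common and add noise to the treatment difference.

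In both cases a 38-subject trial gives up precision that a variable already on record could recover.

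**Working it through.** **Inputs from the documents (Section 10.3).** "A sample size of 19 in each group (total sample size of 38) will have 80% power" to "detect a difference in means of 48", "assuming that the common standard deviation is 50", "using a two-group t-test with a 0.05 two-sided significance level". For pain, the difference is 51 with the same SD.

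**Assumptions.** Four sites of 10, 10, 9 and 9 subjects, all 38 with Day 84 data. A share ρ of the total variance (50²) lies between sites, with total SD held at 50. The documents give no value for ρ, so 0 to 0.30 is shown.

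**Step 1: reproduce the plan's figure.** Noncentrality = 48 / (50 × √(2/19)) = 48 / 16.22 = 2.96. With 36 df, power is 82.1%. At 18 per arm it is 79.9%, so 19 is the smallest sufficient number and the stated sample size reproduces. For pain, 19 per arm gives 86.4%.

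**Step 2: site in the model, allocation balanced within site.** Residual SD = 50 × √(1 − ρ); df = 38 − 2 − 3 = 33.

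| ρ | Residual SD | Noncentrality | Power, height | Power, pain |
|---|---|---|---|---|
| 0 | 50.0 | 2.96 | 81.9% | 86.2% |
| 0.10 | 47.4 | 3.12 | 85.7% | 89.5% |
| 0.20 | 44.7 | 3.31 | 89.4% | 92.7% |
| 0.30 | 41.8 | 3.54 | 92.9% | 95.4% |

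**Step 3: like-for-like comparison for height, balanced within site.** These powers must not be set against the 82.1% of step 1, which assumes no site variance. Under balanced allocation the unadjusted test also gains when part of the fixed total variance moves between sites. Simulation, 12,000 trials per setting:

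| ρ | Power, no site term | Power, site fitted | Change (points) | Type I error, no site term |
|---|---|---|---|---|
| 0 | 82.4% | 82.0% | −0.4 | 4.7% |
| 0.10 | 83.5% | 85.2% | +1.7 | 4.6% |
| 0.20 | 85.1% | 89.4% | +4.3 | 3.4% |
| 0.30 | 87.2% | 92.9% | +5.7 | 2.9% |

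Repeat simulations agree on power to about 1 point. For type I error they range over 4.3–4.6% at ρ = 0.10, 3.4–3.7% at 0.20 and 2.9–3.4% at 0.30. With site fitted it is about 5% throughout. At ρ = 0.30 the mean standard error falls from 15.5 to 13.5 when site is fitted.

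**Step 4: list not blocked within site.** Permuting 19:19 over the same sites gives a 53% chance that at least one site is split 7:3 (of 10), 7:2 (of 9) or worse.

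| ρ | Power, no site term | Power, site fitted | Change (points) | Type I error, no site term |
|---|---|---|---|---|
| 0 | 82.3% | 78.8% | −3.4 | 4.9% |
| 0.10 | 83.1% | 82.3% | −0.8 | 4.8% |
| 0.20 | 84.1% | 87.0% | +2.9 | 4.8% |
| 0.30 | 84.6% | 90.4% | +5.8 | 4.8% |

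Changes are taken before rounding. Other runs put the first row at 78% against 82%.

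**The case against.** The case for leaving the plan alone has real force.

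- **The stated power is not at risk from this.** The unadjusted test has about 82% power or more for height in every setting above. This stands: the fix adds precision and does not repair a shortfall.
- **Validity is not at risk.** A reader might infer from the 53% chance of an uneven split that the result would be biased or the false-positive rate inflated. The figures do not support that. With an unblocked list the unadjusted type I error stays at about 5%, because the standard error already allows for chance imbalance; with a balanced list it is at or below 5%.
- **Between-site variance is conjecture.** A reader might take it that site staff measure the lipomas and that the readings depend on the operator. The documents do not say who acquires or reads the ultrasound. Height is also expressed relative to each lipoma's own baseline, so a constant proportional offset at a site cancels. This stands, and is why ρ = 0 is in the range. Differences in lipoma selection, injection practice or pain rating would not cancel in this way.
- **The ANCOVA and MMRM could include site.** They could, but nothing commits the sponsor to it: the covariates are unnamed and data-driven. This softens the point without answering it.
- **Fitting site can lose power.** True when the list is not blocked and sites differ little (step 4). It argues for linking the two changes, not against both.

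**Conclusion.** The point holds as a low-cost improvement. The plan neither states blocking within site nor commits to site in the patient-level analysis. What is lost is precision: with allocation balanced within site, about 0, 2, 4 and 6 power points for height at site shares of 0, 10, 20 and 30%, with an unadjusted test that becomes mildly conservative as the share rises.

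A larger gain of about 4, 7 and 11 points might be inferred by comparing 86, 89 and 93% with 82%. That comparison mixes site variance in one arm of the contrast with none in the other, and overstates the benefit roughly twofold.

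The size rests on assumed site shares, four near-equal sites, a total SD of 50 and complete data. No like-for-like comparison was run for pain; the same reasoning applies, from a higher starting power of 86.4%.

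**What to change.** Make the two changes together.

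1. **Section 5.2.2:** state that the list is generated in permuted blocks within site.
2. **Sections 10.2.1 and 10.2.2:** prespecify site as a fixed effect in the patient-level model for height and for pain, or use the van Elteren test stratified by site if the analysis is rank-based. Fix a pooling rule before unblinding, for example for any site with fewer than 4 subjects.
3. **Synopsis:** reconcile 3–4 centres with the 4 sites given elsewhere.

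**Cost:** protocol and SAP wording, generation of the list, and 3 error degrees of freedom. At zero site variance that is 0.2 power points by formula (82.1% to 81.9%) and 0.4 by simulation. No subjects or procedures are added.

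**Condition:** if the list is not, or can no longer be, blocked within site, the site term should not be added automatically, since it could cost 3 to 4 points when sites do not differ.
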